## Synopsis

The proposed DIAMA (DIagnostics for Multidrug resistant tuberculosis in Africa) study aims to address current gaps in the diagnosis and management of patients with Multi-Drug-Resistant (MDR) tuberculosis (TB). Building on existing networks and research collaborations, the project aims to evaluate and implement rapid and accurate molecular tests for resistance to anti-TB drugs, to replace the current dependency on phenotypic drug resistance testing (DST), which takes up to 4 months and is technically so demanding that few laboratories can perform these tests correctly.

The project builds on the World Health Organization (WHO) recommended continuous surveillance of patients for rifampicin resistance. Two African partners with advanced molecular laboratories will establish reference laboratories for the 'Deeplex' assay, a novel multiplex deep sequencing-based drug resistance diagnostic platform that simultaneously provides sequence information of genes that confer resistance to key TB drugs. Partners will recruit all patients with RR TB, and a subset of those with rifampicin sensitive TB. In a first phase, sputum will be shipped for the Deeplex assay, for comparison against phenotypic DST to 1st and 2nd line drugs. In a second phase, InSilixa and Cepheid 2nd line Xpert, two 'lower tech' tests at the last stages of laboratory validations, will be implemented in all countries that have established recruitment of retreatment patients. The InSilixa lab-on-chip assay, powered by a smartphone, is able to query 117 drug resistance conferring mutations at around \$20 per test. The Cepheid Xpert 2nd line cartridge can be implemented in existing Xpert machines used for the Xpert MTB/Rif assays. These two tests will be compared versus the Deeplex assay.

Using the latest advances in e-Health software 'DataToCare', molecular results would be communicated in real time to the National TB Programs, so that MDR patients can swiftly start appropriate treatment.

Lastly, once patients have initiated MDR treatment, they will be monitored for treatment success by faster alternative approaches to the WHO recommended monthly cultures: serial sputum samples will have Fluorescein DiAcetate (FDA) vital stain microscopy and measurement of the bacterial load using the Xpert MTB/Rif.

Together, these advances are expected to dramatically improve the currently dismal prognosis of MDR-TB in health systems in resource-poor settings.

## Introduction

### 1. **Background**

#### **Background on MDR-TB diagnosis**

The majority of MDR-TB patients worldwide today are neither detected nor accessing appropriate treatment (1). Recent advances in molecular diagnostics, especially the Xpert MTB/Rif test (2), have reduced the time to diagnose MDR-TB, and improved treatment regimens are rolled-out concurrently (3-5). Despite these advances, many questions remain. Only rifampicin resistance is diagnosed by the Xpert MTB/Rif test, leading to presumptive diagnosis of resistance to isoniazid and maybe other drugs. Resistance to other anti-TB drugs, linked to a range of mutations in other genes, affects the patients' prognosis and optimal treatment composition (6). Unpublished results from Institute of Tropical Medicine (ITM, Antwerp, Belgium) suggest that certain specific mutations in the gyrase gene confer high-level resistance to fluoroquinolones, and are associated with poor MDR TB treatment outcome. Patients with RR TB therefore need treatment adjusted towards other potent drugs. However, assessing resistance to other drugs currently takes weeks to months (7). In the present study, we aim to swiftly and accurately diagnose resistance to rifampicin and other drugs at country and regional levels by:

- Validating a higher complexity assay (Deeplex) that would be available in two regional reference laboratories for the benefit of the whole regions
- Validating lower complexity assays that, albeit less informative, could be available country-wide at district level (Xpert 2nd line) and/or as point of care tests (InSilixa)
- Identifying the thresholds of proportions of drug resistant mutants directly in sputum that predict clinical resistance and poor outcome.
- Informing the potential addition of phenotypically and/or clinically validated mutations identified by Deeplex to the InSilixa point-of-care assay

#### **Technical background – Deeplex assay**

The Deeplex test, developed by Genoscreen (8), consists of a targeted Next Generation Sequencing (NGS) assay, coupling multiplex PCR to deep sequencing. This approach is designed to be directly applicable on clinical samples, providing species- and *M. tuberculosis* lineage identification, and detection of drug resistance. The Deeplex test can simultaneously detect mutations in numerous genes that confer resistance to multiple anti-TB drug classes: The amplicons are deep sequenced on a MiniSeq platform, This molecular assay is coupled to a dedicated secured, cloud-based bioinformatics application, including analysis of deep sequencing data and final reporting of identification of resistance associated mutations. The MiniSeq based Deeplex test however requires specific infrastructure, equipment and technical skills and will only be deployed in well-established reference laboratories such as Laboratoire de Référence des Mycobactéries (LRM, Cotonou), Rwanda Biomedical Center (RBC, Kigali), and ITM in Antwerp. A sample referral system will be set up between the different countries to ensure shipment to the two African laboratories; ITM will serve as a back-up and external referent. Once concurrent phenotypic assays will not be needed any longer in the context of this project, sputum referral systems can include inactivation, such as in ethanol, to facilitate sample shipment (non-infectious, and no cold chain required).. The Deeplex assay will in a second phase also serve for validation of the point of care tests,

as it will detect all mutations in the respective genes. Moreover, it may identify novel mutations, including those unique to strains circulating in Sub-Saharan Africa.

**Table 1.** Antibiotics, and their gene targets, to which resistance is detected in Deeplex

Gene target	Antibiotic	Deeplex
aphC	Isoniazid	+
eis	kanamycin	+
embB	ethambutol	+
ethA	ethionamide	+
fabG1	isoniazid	+
gidB	streptomycin	+
gyrA	Fluoroquinolones*	+
gyrB	Fluoroquinolones*	+
inhA	isoniazid	+
katG	isoniazid	+
pncA	pyrazinamide	+
rplC	linezolid	+
rpoB	rifampicin	+
rpsL	streptomycin	+
rrl	linezolid	+
rrs	Injectable agents	+
tlyA	capreomycin	+

\*including ofloxacin, levofloxacin, moxifloxacin and gatifloxacin

#### **Technical background – InSilixa ‘HYDRA-1K’ chip**

The InSilixa ‘HYDRA-1K’ chip (9) can detect 117 resistance conferring single nucleotide polymorphisms (SNPs), in addition to the wild-type sequence, all in triplicate, in a disposable chip and a hand held reader that can be operated on a smart phone (10). This test, rapid and cheap, including integrated sample processing, is at the last stage of laboratory validation and is expected to be ready for field testing in the second phase of the project. The platform is flexible, like Deeplex, and can have novel SNPs added.

#### **Preliminary results – InSilixa ‘HYDRA-1K’ chip**

InSilixa’s chip has been validated on the WHO Tropical Disease Research (TDR) TB strain collection of 229 strains and showed good results.

Sputum processing will be done in an integrated platform and has been completed successfully on artificial sputum spiked with different concentrations of *Mycobacterium tuberculosis* complex bacteria.

#### **Technical background- Xpert 2nd line**

The Xpert MTB/Rif (developed by Cepheid) has already revolutionized the rapid detection of resistance to rifampicin (2). As this platform is rapidly expanded, and is based on a closed system that limits contamination, a cartridge for 2nd line drugs will be easily implementable and provide rapid indications on resistance to 2nd line drugs. Based on communications by Cepheid representatives, the Cepheid 2nd line cartridge is expected to be released in early

2017. It will be implemented for patients who test RR in the Cepheid Xpert MTB/RIF and will be compared against the Deeplex and InSilixa tests.

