## **4. Sample size**

The partners in the proposal expect to recruit at least 80% of the eligible retreatment patients (those with RIF resistance -considered as MDR- and equal numbers of RIF sensitive patients) presenting for diagnosis and care. Based on previous years data, over 4700 patients at risk of RR TB are on average collectively being screened annually out of which 590 (15%) are diagnosed as being RR-TB (Table 2, in Background).

For the validation of the novel tests (Study 1), we will recruit all RR patients and equal numbers of RIF susceptible patients, for a total of 1420 RR- and 1420 RIF susceptible patients. In the table below, we summarize the power we expect to have to detect resistance to the key drugs:

**Table 3.** Sample size considerations against **phenotypic** gold standard (Phase 1), and the **genotypic** gold standard (Phase 2, see study flow chart in Annex 1), with each phase including 1420 patients, half of whom will have RR TB, for a total of 2840 patients.

Drug	Expected prevalence of resistance in RIF R (n=710 each phase)	Expected total prevalence of resistance (n=1420 each phase)	Expected sensitivity and precision against phenotypic test	Expected specificity and precision against phenotypic test	Expected sensitivity and precision against genotypic test	Expected specificity and precision against genotypic test
RIF	710 (100%)	710 (50%)	98% +/- 1%	98% +/-1%	98% +/- 1%	98% +/-1%
INH	675 (95%)	923 (65%)	90% +/- 1%	98% +/-1%	98 +/- 1%	98% +/-1%
FQ	43 (6%)	43 (3%)	85% +/- 8%	98% +/-1%	98%, range 88%-100%	98% +/-1%

RIF= rifampicin, INH=isoniazid, FQ=fluoroquinolones

The estimated prevalence of resistance is based on the WHO report (1) and personal communications. This sample size will be ample to validate these tests for resistance to RIF, isoniazid, and fluoroquinolones, according to established guidelines (9).

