## 5. Study outcomes

- For the study 1 (validation of deeplex test, Insilixa and Xpert 2nd line):

Drug resistance to INH, RIF, ofloxacin, kanamycin as measured by phenotypic methods and Deeplex method.

Secondary outcome: for both RR- and RS patients programmatic treatment outcome will be recorded.

- For the study 2 (cohort study, on RR patients only):

Three types of unfavorable treatment outcomes will be considered:

- Early treatment failure defined as a culture positive at month 6 of the TB treatment (+/- 2 weeks) not followed by negative consecutive cultures and with molecular confirmation of the similarity of the strain with the baseline one
- End of treatment failure defined as a positive culture at the end of the TB treatment (+/- 2 weeks) not followed by negative consecutive cultures and with molecular confirmation of the similarity of the strain with the baseline one
- Relapse defined as a positive culture after the end of the TB treatment not followed by negative consecutive cultures and with molecular confirmation of the similarity of the relapse strain with the baseline one.

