## **9. Data Analysis**

For the phase I and II of the study 1 (validation of Deeplex against phenotypic DST & validation of InSilixa and Xpert 2nd generation against Deeplex results), we will validate the molecular assays for their performance (Se and Sp) on the diagnosis of RIF resistance, against phenotypic DST on solid medium as gold standard, with resolution of discordances by classic target sequencing of the *rpoB* gene. Similar analyses will be conducted to determine the performance for the diagnosis of isoniazid and fluoroquinolone resistance.

An interim analysis will be performed after 350 RR-TB patients have been recruited in order to test our assumptions regarding resistance proportions and consider adjustment of sample size or recruitment strategy.

For the study 2, the results will be analyzed with time dependent Cox regression to identify the optimal time point to identify patients who are at risk of failing treatment.

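### The plan does not settle who is tested with the Xpert 2nd line cartridge; if RR patients alone, RIF specificity cannot be estimated and Table 3's INH precision does not apply

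*Combined protocol and SAP*

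**What the plan says.** **Who is tested.** The Introduction (Technical background, Xpert 2nd line) presents the cartridge as a product for second-line drugs. On its use it says: "It will be implemented for patients who test RR in the Cepheid Xpert MTB/RIF". It adds that results will be compared with Deeplex and InSilixa. It does not list the drugs reported.

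The Methods sections set no RR limit. Section 1 (Study design) compares InSilixa and Xpert 2nd generation with Deeplex in the Study 1 population, which includes RIF-susceptible retreatment patients. Section 6 (Data collection) records both tests for phase 2 and does not put the cartridge among the RR-only items. Section 8 (Specific tests) stores surplus sputum for both tests without restricting it to RR patients.

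**What is analysed.** Section 9 opens with both phases, naming InSilixa and Xpert 2nd generation, and continues: "we will validate the molecular assays for their performance (Se and Sp) on the diagnosis of RIF resistance". Then: "Similar analyses will be conducted to determine the performance for the diagnosis of isoniazid and fluoroquinolone resistance". It gives no separate population or drug list for the cartridge.

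**What precision is stated.** Section 4 describes Table 3 "with each phase including 1420 patients, half of whom will have RR TB". The column headed "Expected specificity and precision against genotypic test" gives 98% ±1% for RIF, INH and FQ alike. No row or denominator is specific to the cartridge.

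**Why it counts.** Validating the cartridge is primary objective 1c.

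**The concern.** Specificity needs patients who are susceptible by the reference test. Table 3 draws its RIF-susceptible patients, and nearly all its INH-susceptible ones, from the RIF-susceptible half of the sample. If the cartridge is run in the RR half alone, that supply is gone, yet sections 4 and 9 read as if all phase 2 assays share the same 1420 patients and the same three drugs.

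The risk is a report on a primary objective that either shows a RIF specificity with no proper denominator or carries over a ±1% that the tested patients cannot support. The Rationale says the companies will use these results in applications for regulatory approval and WHO endorsement, so each assay's population and drugs should be unambiguous.

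**Working it through.** **Inputs from Table 3 (each phase).** 1420 patients, 710 of them RR. INH-resistant: 675 of the 710 RR, 923 of all 1420. FQ-resistant: 43, all RR. Expected specificity 98% ±1% for each drug. The confidence level is not given; I assume 95%.

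**Formula.** Half-width = 1.96 × √(p(1 − p)/n), with p = 0.98, so p(1 − p) = 0.0196.

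**Step 1: reproduce the stated specificity precision on all 1420.**
- RIF: n = 1420 − 710 = 710; 1.96 × √(0.0196/710) = 1.03 points.
- INH: n = 1420 − 923 = 497; 1.96 × √(0.0196/497) = 1.23 points.
- FQ: n = 1420 − 43 = 1377; 0.74 points.

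All three round to the printed ±1%. For RIF and INH this works only with the RIF-susceptible half included.

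**Step 2: repeat with the 710 RR patients only.**

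| Quantity | n, all 1420 | n, RR only | Half-width, RR only |
|---|---|---|---|
| RIF specificity | 710 | 0 by the entry test | not estimable |
| INH specificity | 497 | 710 − 675 = 35 | ±4.64 |
| FQ specificity | 1377 | 710 − 43 = 667 | ±1.06 |
| FQ sensitivity | 43 | 43 | unchanged |

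- **RIF.** Some RR patients may be RIF-susceptible by Deeplex. The documents give no rate. Assuming 1% to 5% of 710 gives 7 to 36 patients and half-widths of about ±10.4 to ±4.6. Every one of them would already be discordant with Xpert MTB/RIF, so they are not a sample from which to claim specificity.
- **INH.** With 34 of 35 correct, the exact 95% interval is 85.1% to 99.9%. The phase 2 reference is Deeplex, so as a check I apply Table 3's expected Deeplex performance against phenotypic testing (sensitivity 90%, specificity 98%). Deeplex-negative RR patients are then 710 − (0.90 × 675 + 0.02 × 35) = 101.8, or about 102, giving ±2.7. Neither figure is ±1.
- **INH patients needed.** A half-width of 1 point takes 1.96² × 0.0196/0.01² = 753 INH-susceptible patients. At 5% INH-susceptible among RR, that is about 15,060 RR patients against 710 planned.
- **FQ.** For sensitivity, 42 of 43 gives an exact interval of 87.7% to 99.9%, matching the printed 88% to 100%.

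**The case against.** The strongest reply is that the RR restriction is inferred. The sentence sits in a technical background paragraph, does not contain the word only, and does not define the validation sample. Sections 1, 4, 6 and 8 carry no RR limit. This stands: a reader might take RR-only testing as settled, and the documents do not support that. They conflict, and the arithmetic above is conditional on one side of the conflict.

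Second, section 9 is one generic paragraph for three assays. Its RIF sentence names phenotypic testing as the reference, and section 6 collects phenotypic results in phase I only, so the sentence fits Deeplex best. A reader might infer that RIF is the cartridge's lead analysis; objective 1c sets no RIF target, so that goes too far. But section 9 does name Xpert 2nd generation in its opening and never exempts it, so the ambiguity remains.

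Third, the documents do not list the cartridge's drugs. If it does not report INH, INH precision is moot; if it does, specificity is imprecise but can be estimated. It would be wrong to call it undeliverable.

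Fourth, Table 3 is organised by drug and does not promise precision per assay, and FQ, its only second-line drug, survives the restriction. That is correct and narrows the point. It does not tell the reader which Table 3 figures apply to the cartridge.

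**Conclusion.** The point holds as an inconsistency with a conditional consequence. The background sentence and the phase 2 sections disagree on who is tested with the cartridge, and section 9 assigns it the same drug list as the other assays. If testing is confined to RR patients, RIF specificity cannot be estimated and any INH specificity has a half-width of about 4.6 points on 35 patients, instead of the stated 1. FQ specificity (667 patients, ±1.06) and sensitivity (43 patients) stand.

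This rests on Table 3's prevalences, a 95% level and 98% specificity. The RIF conclusion does not depend on the assumed 1% to 5%.

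Kanamycin is a separate, minor matter. Section 5 lists the Study 1 outcome as "Drug resistance to INH, RIF, ofloxacin, kanamycin as measured by phenotypic methods and Deeplex method", while neither Table 3 nor section 9 mentions kanamycin. A reader might infer that one of the cartridge's own target drugs lacks an analysis. The documents do not support that: they name no cartridge targets, and this outcome concerns phenotypic and Deeplex results. It is a missing detail about a Study 1 outcome.

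**What to change.** Reconcile the background paragraph on the cartridge with sections 1, 4, 6 and 9, and state the tested population and reported drugs for it.

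- **If RR patients only:** say in section 9 that the cartridge is assessed against Deeplex, and compared with InSilixa as the background plans, in RR patients, for the drugs it reports, with no RIF specificity claim. Give it its own denominators in Table 3: FQ on 710 RR patients (43 resistant, 667 susceptible), and INH only if reported, at about ±4.6.
- **If all 1420:** correct the background sentence and keep Table 3 for the drugs the cartridge reports.
- **Separately:** say whether the kanamycin outcome in section 5 gets an accuracy analysis or is descriptive. An accuracy analysis needs an assumed prevalence, labelled as such, because the documents give none.

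Under the RR-only option these are wording and table edits needing no extra patients. The price is a narrower claim for the cartridge.

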### **Background on continuous surveillance**

WHO recommends to perform continuous surveillance for rifampicin resistance among retreatment patients, in whom such resistance occurs in around 15-20% in most Sub Saharan African settings (1). This tends to be done using the Xpert MTB/Rif, which in most settings is highly sensitive for rifampicin resistance, yet does not detect additional resistance to other antibiotics. The Xpert moreover misses the *rpoB* mutations outside of the test region, of which mainly the *rpoB572* mutation is clinically relevant and is included in the novel assays tested in this proposal.

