### 1. Study design:

Two multi center observational studies will be conducted:

- *Study 1:* Cross sectional study for TB cases aged  $\geq 15$  (all RIF resistant (RR) ones (new cases or retreatment patients) and equal number of RIF sensitive retreatment

patients from the same country) with comparison of TB resistance diagnostic test performance at baseline. There are 2 phases in this project; phase 1 is the comparison of Deeplex results against the phenotypic results (Gold standard), phase 2 is the comparison of Insilixa and Xpert 2nd generation results against Deeplex (gold standard).

- *Study 2:* Cohort study of RR-TB patients (recruited in Study 1) under treatment with comparison of the performance of FDA or Xpert compared to solid culture

The study flow chart is placed in annex 1 of this protocol

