## **2. Study settings**

The study takes place in nine African countries (Benin, Cameroon, DRC, Ethiopia, Guinea, Mali, Nigeria, Rwanda and Senegal) with patients recruited at a national or regional level (depending on country size), and the samples tested in the respective reference laboratory (see partners). All partners involved in this study have or will implement(ed) a routine system of screening all TB patients at risk for resistant TB aged  $\geq 15$  with Xpert/MTbRif.

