## **3. Study population**

In order to be eligible for study 1 and 2, study participants **must meet the following criteria:**

- Being  $\geq 15$  year old
- Having a positive test on GeneXpert (*M. tuberculosis*) with or without resistance detected to rifampicin
- Willing and able to provide written informed consent, or for minors: assent from these patients and consent from a legal representative

In addition, for the study 2 (cohort study), only patients for whom RIF resistance was detected with GeneXpert at baseline and who started MDR-TB treatment will be eligible.

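### Study 1 selects patients on the Xpert rifampicin result, so the planned pooled RIF sensitivity mostly measures agreement on resistance Xpert has already found and says little about resistance Xpert misses

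*Combined protocol and SAP*

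**What the plan says.** - **Claimed advantage.** Background on continuous surveillance: Xpert misses rpoB mutations outside its region. Of these, mainly the rpoB572 "mutation is clinically relevant and is included in the novel assays tested in this proposal".
- **How RIF status is set.** Methods 2 describes "a routine system of screening all TB patients at risk for resistant TB" by Xpert. Methods 3 admits Xpert-positive patients "with or without resistance detected to rifampicin". Study 2, whose patients are the RR patients of Study 1, takes "only patients for whom RIF resistance was detected with GeneXpert at baseline". No other test is named for assigning RIF status at entry.
- **Sampling.** Methods 1 enrols "all RIF resistant (RR) ones (new cases or retreatment patients) and equal number of RIF sensitive retreatment" patients from the same country. Methods 4 repeats that "we will recruit all RR patients and equal numbers of RIF susceptible patients", "with each phase including 1420 patients, half of whom will have RR TB, for a total of 2840 patients".
- **Planned precision.** The RIF row of Table 3 puts resistance at 710 (100%) in the RR half and 710 (50%) overall, with sensitivity and specificity each 98% ± 1%.
- **Analysis.** Methods 9 plans RIF sensitivity and specificity "against phenotypic DST on solid medium as gold standard", with rpoB sequencing of discordant results. It plans no breakdown by Xpert result and no weighting for the 1:1 sampling.
- **Reference data.** Methods 6 lists phenotypic DST for all patients, but in phase I only. Methods 1 makes Deeplex the phase 2 reference.

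**The concern.** The selecting test and the test under study are not independent. Xpert reads part of rpoB, and Table 1 shows that Deeplex also calls rifampicin resistance from rpoB. Taking every patient whom one rpoB test called resistant fills the sensitivity denominator with cases in which such a test has already succeeded. Resistance that Xpert misses can enter only through the susceptible half, which is sampled much more thinly.

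A pooled, unweighted figure would naturally be read as the assay's accuracy against phenotypic DST in the patients screened. The Rationale says the results will go into regulatory applications and WHO endorsement, so that reading matters. The pooled figure would also hardly change whether or not the assay finds the mutations the Background credits to it.

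**Working it through.** **1. The plan's own figure.** With sensitivity 0.98 and n = 710 (95% level assumed; none is stated), the half-width is 1.96 × √(0.98 × 0.02 / 710) = 1.03%. This reproduces the printed ± 1% from the 710 Xpert-detected cases alone.

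**2. Resistance expected in the susceptible half** (Table 3 total minus RR column). RIF: 710 − 710 = 0. For contrast, INH: 923 − 675 = 248.

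**3. Under-representation.** The study enrols 1 susceptible patient per RR patient. The source has r susceptible patients per RR patient:
- Background, 15–20% resistance among retreatment patients: r = 0.80/0.20 = 4.0 to 0.85/0.15 = 5.67.
- Methods 4, 590 RR of 4700 screened: r = (4700 − 590)/590 = 6.97. Methods 4 prints 15% for this, but 590/4700 is 12.6%.

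An Xpert-missed case therefore carries about one quarter to one seventh of its source weight.

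**4. Effect on sensitivity.** Let p be the share of Xpert-susceptible patients who are RIF-resistant and s the assay's detection in them, with 98% detection in Xpert-RR patients. As a simplification, all 710 Xpert-RR patients are taken as truly resistant.
- Unweighted: (0.98 + s·p)/(1 + p)
- Weighted to source: (0.98 + s·r·p)/(1 + r·p)

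The documents give neither p nor s. The range p = 0.5–2% (about 4 to 14 of 710) is an assumption.

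| p | s | r | Unweighted | Weighted | Gap (points) |
|---|---|---|---|---|---|
| 0.5% | 50% | 4.0 | 97.8% | 97.1% | 0.7 |
| 1% | 50% | 5.67 | 97.5% | 95.4% | 2.1 |
| 2% | 0% | 5.67 | 96.1% | 88.0% | 8.1 |
| 2% | 90% | 5.67 | 97.8% | 97.2% | 0.7 |
| any | 98% | any | 98.0% | 98.0% | 0 |
| 2% | 100% | 5.67 | 98.0% | 98.2% | −0.2 |

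With r = 6.97 the most extreme row (p = 2%, s = 0) becomes 96.1% against 0.98/1.139 = 86.0%, a gap of 10.1 points.

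**5. Can the pooled figure tell assays apart?** At p = 1%, an assay that finds no missed case shows 0.98/1.01 = 97.0%. One that finds all of them shows 0.99/1.01 = 98.0%. The difference is about one half-width of the printed interval.

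**6. What the susceptible half can show alone.** If every missed case is detected, the exact 95% lower limit is 0.025^(1/n): 16% for 2 of 2, 40% for 4 of 4, 48% for 5 of 5. As a cross-check on the counts, an assumed Xpert sensitivity of 95% gives 590 × 0.05/0.95 = 31.1 missed cases a year among 4110 susceptible patients, or 710 × 31.1/4110 = 5.4 per phase. Assumed sensitivities of 99% and 90% give about 1.0 and 11.3.

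**The case against.** Several objections carry weight and limit the point.

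- **Verification bias.** A reader might infer this, but the documents do not support it. In phase 1 all patients are listed for phenotypic DST, so reference testing does not depend on any index result, and an Xpert-missed case that is enrolled will be counted. The problem is selection on a correlated test.
- **Sensitivity necessarily too high.** This too might be inferred, and does not follow. The technical background describes Deeplex as covering every mutation in its target genes, and the surveillance background says rpoB572 is included. If that holds in practice, s is near 98% or above and the gap vanishes or slightly reverses.
- **Specificity pushed down.** Xpert-RR, phenotypically susceptible patients who share an rpoB call could lower it. But Methods 9 sends discordances to rpoB sequencing without giving the reclassification rule. The effect on specificity is uncertain, and no size is claimed here.
- **Not an objective.** Detecting Xpert-missed RIF resistance is not among the listed objectives or outcomes, and Table 3 is a planning table. The trial does not fail a stated aim. Still, RIF accuracy is a planned result, and its interpretation depends on the sampling.
- **Weighting has limits.** RR patients may be new or retreatment cases, whereas susceptible patients are retreatment only. New susceptible patients are never sampled, so no weight can represent them. The 15–20% figure also strictly applies to retreatment patients only.

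The missing breakdown by Xpert result and the absence of weighting still stand.

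**Conclusion.** The point holds as one about selection and interpretation, for RIF only. INH and FQ resistance are not selected through their own genes. The 98% ± 1% describes sensitivity in Xpert-detected resistance. The 4- to 7-fold under-representation follows from the documents' own figures, on the reading that RR status at entry means the Xpert result.

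The size and sign of any bias in sensitivity cannot be settled from the documents. The range of 0.7 to 8.1 points upward requires the assumed p of 0.5–2% and s of 0–50% with r of 4.0–5.67. What is secure is that the pooled figure can hardly show whether the assays find Xpert-missed resistance, and that the few such cases likely to be enrolled would give only a wide interval. In phase 2, with Deeplex as reference and no phenotypic DST collected, resistance that Deeplex misses cannot appear at all. The change should be made: it alters what can be concluded about RIF at almost no cost.

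**What to change.** In Methods 9 and the RIF row of Table 3:

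1. Report phase 1 RIF accuracy by Xpert stratum, and state that the 98% ± 1% sensitivity applies to Xpert-detected RIF resistance.
2. For phase 1, report with exact intervals how many Xpert-susceptible patients are RIF-resistant by phenotypic DST, before and after rpoB sequencing, and how many of these Deeplex detects. For phase 2, state that the same table is relative to Deeplex and cannot show resistance that Deeplex misses.
3. If one overall RIF sensitivity and specificity is given, restrict it to retreatment patients and weight the Xpert strata by screened/enrolled counts per country.
4. Make no claim about Xpert-missed RIF resistance beyond item 2.

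**Cost.** Revised analysis wording, one extra table, and per-country counts of retreatment patients screened by Xpert result. This assumes routine records hold retreatment status for everyone screened, which the documents do not confirm. Any overall RIF interval will be wider than ± 1%. No additional patients, samples or tests are needed.
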